8.3.4 Patient and provider in-depth interviews

In-depth interviews will be conducted at the end of the study period with approximately 20 patients and 15 care team members who have used the Pathway Platform. Interviews will involve discussing reactions and feedback on the Pathway Platform, education material, care team interface, and overall implementation of the Pathway Platform. These semi-instructed in-depth interviews will allow patients to reflect on the process and identify higher level causes behind any difficulties or challenges, explore any suggested changes and to gather general feedback regarding the participant's experience during the study. Findings from this sub-study will complement the main study analysis and explore the use of the Pathway Platform App and what this could mean for ongoing development of the Pathway Platform.

8.3.5 System level performance

Performance and patient outcomes evaluated in this study will be evaluated at the system level covering all primary care clinics. Data will be collected retrospectively on patients attending any primary care clinic during the study period. This data will be used to understand performance at the system level.

8.4 Data analysis

For primary and secondary hypothesis testing, process measures, patient clinical outcomes, and health care resource utilization will be compared pre- and post- implementation of the Pathway Platform.

Additional patient reported outcomes will be compared among patients using the Pathway Platform only at baseline and end of study. For pre-implementation, outcomes will be assessed among patients who visited one of the study clinics at least once over the pre-implementation study period and were eligible to use the Pathway Platform, if it had been available. For the post-implementation period, the Pathway Platform will be the data source for paired t-test analysis, assessing change in continuous variables including PHQ-9 scores. Categorical outcomes will be presented as proportions and compared using Pearson Chi2 test. Continuous outcomes will be assessed for normality and presented as means and standard deviations (SD) or medians and interquartile ranges (IQR); continuous outcomes will be compared using Student's t test for independent groups. Two-tailed tests using a significance threshold of $p < 0.05$ will be used for all tests.

Exploratory outcomes: will be described among patients attending the pathway platform clinics only and will be compared between baseline, 6-month and extended follow up. Change in these outcomes overtime, including utilization analytics will also be explored. Categorical outcomes will be presented as proportions and compared using McNemars' test. Continuous outcomes will be assessed for normality and presented as means and standard deviations (SD) or medians and interquartile ranges (IQR); continuous outcomes will be compared using Student's Paired t test for single group comparison. Two-tailed tests using a significance threshold of $p < 0.05$ will be used for all tests. Goal attainment will be summarized by proportion of patients who achieve their identified goals based on the set time bound duration of the goal (i.e., GAS Score ≥ 50).^{29,30} The goal attainment scale adapted for depression yields a norm-based score (standardized to a mean of 50, SD of 10) at baseline and at the end of the time bound goal; the change from score from baseline will also be summarized.

System level performance: Process outcomes will be evaluated at the system level (all primary

care clinics) among patients fulfilling eligibility criteria, if the app were available. Descriptive analysis will be utilized to describe process outcomes across all clinics.

In depth interviews: Interpretative Phenomenological Analysis will be used to analyze the qualitative data. To increase the rigor and validity of the analysis, and as a form of triangulation, the analysis will be conducted by 3 members of the research team (the lead qualitative researcher and 2 others). Analysis will involve 2 stages: (1) Data management, which will include, familiarization with the data, reading notes, and/or listening to the audio dialogue in order to extract main themes and ideas and thematic framework development, identifying the key issues and concepts present in the data and creating themes both inductively, based on the data, and deductively, based on the research questions, (2) Interpretation stage, which will include focused defining the main concepts and mapping the ways in which different parts of the data are related to each other.

4. 9.4 PARTICIPANT RIGHTS AND CONFIDENTIALITY

4.1 9.4.1 Institutional Review Board (IRB) Review

This protocol, the informed consent document, and any subsequent modifications will be reviewed and approved by the Advocate's IRB, who is responsible for oversight of the study.

4.2 9.4.2 Informed Consent Forms

A signed consent form will be obtained from each participant by the Advocate Research Team. The consent form will describe the purpose of the study, the procedures to be followed, and the risks and benefits of participation. A copy will be given to each participant and will be documented in the participant's record.

4.3 9.4.3 Participant Confidentiality

Data will be extracted from an EMR data pull as well as chart reviews and shared only with the clinic and research staff that are needed to identify eligible patients for the study in a password-protected MS Excel sheet. For clinic staff, shared patient information will be limited to only the patients seen at that clinic location. All paper copies of study data collection forms will be stored in a secure location at Advocate Research Institute to maintain subject confidentiality.

A subject ID will be assigned to each study participant; this will serve as a unique subject identifier for the study and Pathway Platform data. Data management for Pathway Platform data will have security processes in place that are service organizational control

or SOC2 compliant. This comprises data storage and transmission between the Pathway Platform, servers, and EMR system. Data collected for the study will be maintained and monitored while the study is active and the identifying link will be destroyed upon study close.

4.4 9.4.4 Study Discontinuation

The study may be discontinued at any time to ensure that research patients are protected.

5. 10. TAKEDA MARKETED PRODUCT ADVERSE EVENT REPORTING REQUIREMENTS

An AE is any untoward medical occurrence in a subject administered a Takeda medicinal product and which does not necessarily have to have a causal relationship with this treatment. An AE can therefore be any unfavorable and unintended sign (including an abnormal laboratory finding), symptom, a new disease or worsening in severity or frequency of a concomitant disease, temporally associated with the use of a Takeda medicinal product, whether the event is considered causally related to the use of the Takeda product.

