3.1 Performance among participating clinics post-implementation

The Pathway Platform will be implemented in up to 20 primary care sites within the Advocate Aurora Health system and enroll a total of 200 patients for six-month duration. The visit where the patient has been onboarded to the Pathway Platform will be the enrollment visit (Figure 1). During the post- implementation period, data on patient outcomes will be collected through the Pathway Platform. At the end of the study an electronic and manual chart review for patients using the Pathway Platform will be conducted among participating clinics and performance related to measurement-based care, shared decision making and collaborative care, where applicable, will be assessed over the post-implementation period.

3.2 Retrospective Assessment: pre-implementation performance at the clinic level (before Pathway Platform implementation)

To assess Advocate's primary care sites performance pre-implementation, an electronic and manual chart review will be conducted from the same Advocate primary care clinics participating in the implementation study. Patients with a clinic visit at least 6 months prior to implementation (index visit) of the Pathway Platform and meeting the inclusion criteria for enrollment in the study, will be included in this analysis (figure 1). Patient history will be evaluated for three months prior to index visit to confirm eligibility. The goal is to capture patients with a new start, dose adjustment or switch of an antidepressant medication 6 months prior to the implementation index date (three-month inclusion window for patient identification). Six months of patient history will be “retrospectively” collected for this baseline patient cohort to assess the primary outcome, defined as PHQ-9 utilization, and other secondary outcomes outlined in the protocol. This analysis will serve as the comparison control for the primary and secondary outcomes to compare performance at the same clinics pre and post-implementation of the Pathway Platform. Depending on the number of eligible patients identified per site (20 per site), group level matching for age and sex may be conducted. The primary endpoint will be the proportion of patients with at least 2 PHQ-9 scores.

Figure 1: Study schematic

* Primary and secondary outcomes will be evaluated at 6 months, data collected beyond 6 months will be used for exploratory analysis

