3.3 Study Duration

Patients will be enrolled in the study for a minimum duration of 6 months with the option to continue using the app at that time to a common study end date of January 7, 2023 (access to in-app final study evaluations will end January 21, 2023). Data from the Pathway Platform will be collected prospectively for the duration of the patient's participation. Process measures will be collected retrospectively from the EMR and through manual chart review after 6 months of enrollment and at the end of the study(post-implementation) and over a 6-month period prior to implementation (pre-implementation).

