*If during the conduct of the study, a health care professional or patient spontaneously reports an Adverse Event or a serious adverse event to a Takeda product; such information should be reported to the sponsor. As such reports are spontaneously notified, causality of any AEs should be assumed unless there is evidence to the contrary; **CollaboRATE will also be asked within the App at Day 84 with a 30 day window for completion during patient enrollment. ***PAM 13, CollaboRATE and WSAS; the App will trigger response to these questionnaires every 6 months until study end (note; if patient completed these questionnaires within 4 weeks of study end point, they will not be re-deployed for completion at end of study).

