- Diagnosis progress notes stating change from mild, moderate, or severe, to in remission or partial remission will be assessed descriptively.

Patient reported outcomes: The difference in scores between baseline, and 6-month follow up will be compared among patients using the Pathway Platform who completed the following measures:

- PAM-13
- CollaboRATE (this questionnaire is also included as a 3-month post-enrollment assessment and will be analyzed across all available time points)
- WSAS

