8.3.3 Exploratory outcomes

Patient clinical and reported outcomes:

- The following patient reported outcomes will be collected in the Pathway Platform throughout the study. The difference in scores between the baseline measure, 6-months, and end of the study will be compared. This will be restricted to patients who completed these scales at these two-time points. To be inclusive of all patients, additional analyses will be conducted to compare first and last scores available:
 - PHQ-9
 - WHO-5
 - PDQ-D5

- The following patient reported outcomes will be collected in the Pathway Platform and described at 6-months and end of the study:
 - Antidepressant Medication adherence
 - Antidepressant Medication dose adjustment and switches
 - Side effects
 - Depression remission
 - Depression response
 - Goal attainment
- Patient reported outcomes (PAM-13, CollaboRATE and WSAS) will also be explored at 6 months and end of the study.

Pathway Platform and report utilization: Pathway Platform analytics will be explored to understand patient adherence to the platform which includes frequency of logging into the Pathway Platform and frequency of completing each of the Pathway Platform functionalities. Care-team utilization of Pathway Platform reports will also be explored, including describing type of care team members who viewed the Pathway Platform reports as well as frequency of viewing the reports.

Education utilization: Frequency of viewing material in the resource education center will be described by patient and by care-team members. Commonly viewed educational material will be highlighted.

Subgroup analysis: primary, secondary, and exploratory outcomes will be compared across a number of patient demographic and clinical characteristics, including PHQ-9 severity at baseline, comorbidities (see appendix 3 for comorbid conditions and ICD codes), app utilization by patients, and EMR report utilization by providers. Additional subgroup analysis will be conducted by type of care model at the site level (e.g. collaborative care vs. non collaborative care sites).

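### Section 8.4 places the secondary patient-reported comparison at end of study, while section 8.3.2 and the Figure 1 footnote place it at 6 months

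*Combined protocol and SAP*

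**What the plan says.** Section 8.3.2 lists PAM-13, CollaboRATE and WSAS as secondary patient-reported outcomes and defines the comparison: "The difference in scores between baseline, and 6-month follow up will be compared among patients using the Pathway Platform who completed the following measures". It adds a 3-month CollaboRATE assessment, to be analysed with all available time points.

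The footnote to Figure 1 (end of section 3.2) gives the general rule: "Primary and secondary outcomes will be evaluated at 6 months, data collected beyond 6 months will be used for exploratory analysis". Section 8.3.3 then lists the same three scales among the exploratory outcomes: "Patient reported outcomes (PAM-13, CollaboRATE and WSAS) will also be explored at 6 months and end of the study".

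Section 8.4, in its text on primary and secondary analyses, says: "Additional patient reported outcomes will be compared among patients using the Pathway Platform only at baseline and end of study". Change in continuous measures from the app is to be tested with paired t-tests, with p < 0.05 as the threshold for every test.

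On timing, the Study Duration section (numbered 3.3, placed after 4.4.3) says: "Patients will be enrolled in the study for a minimum duration of 6 months", with optional continuation to a "common study end date of January 7, 2023". Table 1 has one column for Day 168-172 and another for study end. Its notes open the three research scales at Day 172 for 30 days, repeat them every 6 months, and add: "if patient completed these questionnaires within 4 weeks of study end point, they will not be re-deployed for completion at end of study".

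**The concern.** One secondary analysis has two follow-up time points. The section that defines the outcome says 6 months; the section that says how it is analysed says end of study. Both would be tested at p < 0.05, so without a correction the choice could be made after the data are seen.

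The two are not interchangeable. The 6-month assessment comes at about the same elapsed time for everyone. A calendar end date comes later for early enrollees than for late ones, and only those who opted to continue can supply a later score. A mean change at that date depends partly on the accrual pattern and on self-selection, and could not be reported as a 6-month change.

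A smaller, separate issue arises in the exploratory comparison of 6 months with end of study. Under the 4-week rule some late enrollees will have a single response where two time points are planned, and the plan does not say how that response is classified.

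**Working it through.** The plan gives no figure to reproduce here. The check is a cross-reading followed by date arithmetic.

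**Step 1. The time points side by side**

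| Place | Role | Time point |
|---|---|---|
| 8.3.2 | Secondary outcome definition | Baseline and 6 months (CollaboRATE also at 3 months) |
| Figure 1 footnote | Rule for primary and secondary outcomes | 6 months; later data exploratory |
| 8.3.3 | Exploratory use of the same scales | 6 months and end of study |
| 8.4 | Analysis of primary and secondary outcomes | Baseline and end of study |

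8.4 does not name the scales. That it means these three is an inference, but a reasonable one: they are the secondary outcomes that 8.3.2 assesses in app users alone, and the exploratory scales have their own paragraph in 8.4.

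**Step 2. What end of study means.** 8.3.3 and Table 1 treat it as distinct from 6 months, and the Study Duration section ties it to 7 January 2023. Section 5.2 lets a patient's participation end at 6 months, at the common end date or at withdrawal, so some patients will have no score at the calendar end.

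**Step 3. Spread of follow-up at the calendar end**
- Latest Day 1 for which Day 172 is reached by the end date: 7 January 2023 − 171 days = 20 July 2022.
- Shortest follow-up: 172 / 30.44 = 5.7 months.
- Longest follow-up for an accrual period of m months: 5.7 + m.

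**Step 4. Patients with one response under the 4-week rule**
- The 4-week window opens on 7 January 2023 − 28 days = 10 December 2022.
- Day 172 falls in the window if Day 1 is between 10 December − 171 days = 22 June 2022 and 20 July 2022, a 28-day span.
- A patient who uses the full 30 days (to Day 202) can answer in the window if Day 1 is on or after 10 December − 201 days = 23 May 2022, a 58-day span.
- Share affected = span / (30.44 × m).

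The accrual length is not in the documents. The table assumes uniform accrual ending 20 July 2022, with every patient continuing and 200 enrolled.

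| Assumed accrual (months) | Follow-up at study end (months) | Share if answered promptly | Ceiling if answered late |
|---|---|---|---|
| 3 | 5.7 to 8.7 | 31% (61) | 64% (127) |
| 6 | 5.7 to 11.7 | 15% (31) | 32% (64) |
| 12 | 5.7 to 17.7 | 8% (15) | 16% (32) |
| 18 | 5.7 to 23.7 | 5% (10) | 11% (21) |

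If the 6-month minimum is read as six calendar months, the last Day 1 is 7 July 2022. The spans shrink to 15 and 45 days. For 12 months of accrual the shares become 15 / 365.3 = 4% and 45 / 365.3 = 12%.

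**The case against.** The best defence is that the plan already settles the matter. The Figure 1 footnote is explicit, 8.3.2 agrees with it, and 8.3.3 puts end-of-study values under exploratory outcomes. The phrase in 8.4 is undefined there and may be loose wording for the close of the 6-month period; 8.3.2 uses a similar phrase for remission, another secondary outcome. This stands as evidence of intent and shows which way to correct the text. It does not remove the conflict, because 8.4 is the section an analyst would follow, and elsewhere the plan uses end of study for a later, separate time point.

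A reader might infer from the 4-week rule that the secondary change repeats the 6-month score, or contains zero differences by construction. The documents do not support this. The rule says only that the scales are not deployed again; nowhere is the earlier answer carried forward to study end, and the later value may simply be missing. Even if the answer were reused, a baseline-to-end difference would not become zero. Zeros could arise only in the exploratory comparison of 6 months with end of study, and only if one response were entered twice.

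A reader might also want a fixed percentage for the resulting dilution. None can be defended: it would need both that undocumented carry-forward and an accrual period the plan does not give.

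Finally, these are uncontrolled, single-cohort measures, so the stakes are modest. That is fair.

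**Conclusion.** The contradiction is real. 8.4 is the outlier against 8.3.2 and the Figure 1 footnote, and should be corrected before analysis. Followed literally, it would replace a 6-month change with one measured over mixed follow-up that depends on enrollment date and on who continued. The size of that mixing cannot be determined; the 5.7 to 23.7 month span is the widest of the illustrative scenarios and rests on assumed accrual.

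The single-response problem is confined to the exploratory comparison and to patients who answered within 4 weeks of the end date. The primary outcome and all comparisons between the pre- and post-implementation cohorts are untouched.

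The conclusion assumes that the sentence in 8.4 refers to PAM-13, CollaboRATE and WSAS, and that end of study there has the meaning it has in 8.3.3, Table 1 and the Study Duration section.

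**What to change.** - In 8.4, for PAM-13, CollaboRATE and WSAS, replace the reference to baseline and end of study with baseline and the 6-month assessment (Day 172, 30-day window).
- Keep CollaboRATE's 3-month assessment and its analysis across all available time points, as in 8.3.2, so that the edit does not create a new inconsistency.
- State in 8.4 that end-of-study values of these scales are exploratory, in line with 8.3.3 and the Figure 1 footnote.
- For the exploratory comparison of 6 months with end of study, include only patients with a separate later administration, and state that one response is not used for both time points.

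There is no need to re-anchor the exploratory follow-up to set months since enrollment; that would be a preference about an analysis the plan already labels exploratory.

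The cost is a wording change, with no new data or patients. The downside is fewer patients in the exploratory comparison.

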4.1 Inclusion

1. Adult aged 18 and above

2. Diagnosis with major depressive disorder or reference to “clinical depression” in patient charts. See **Appendix 1** for ICD codes for major depressive disorders
3. Recently prescribed monotherapy antidepressant medication (defined as new start, medication switch, or dose change in the past 3 months (**Appendix 2**).
4. Patients with inadequate response or tolerability concerns determined based on A PHQ-2 score of 3 or greater, or a PHQ-2 <3 with a PHQ-9 score of 5 or greater recorded in medical records in the past 6 weeks or during screening,
5. Able and willing to provide informed consent
6. Able to use the Pathway Platform based on clinician’s judgment, e.g. owns an iPhone version 5 or later or smartphones with Android operating systems, have an active data plan or regular WiFi access.

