4.4.3 Educational Scaffolding

An online Educational training program was developed using evidence-based medicine building

on measurement-based care and shared-decision making concepts as they relate to depression management. Educational material describes how the Pathway Platform can help care team members in clinical processes related to these process improvement measures. In clinics using a collaborative care model additional education material specific to this care model is provided. Educational material housed in an online resource center which includes reading material, presentations, and videos. Additionally, up to three audit and feedback sessions will be conducted for each participating clinic. The objectives of audit and feedback sessions are to benchmark performance measures, including shared decision making, reflect on current clinical practice and improvement strategies, and setting team-based action plans. Care team members who manage depression must complete specific training before they are able to enroll patients and begin using the Pathway Platform.

A training manual was also developed for patients. The manual describes the Pathway Platform functionality, as well as, how to use and interpret the data collected.

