8. STATISTICAL CONSIDERATIONS

8.1 General Design and Hypothesis

The following hypotheses will be examined:

Primary hypothesis: PHQ-9 utilization will be greater after implementation compared to before implementation of the Pathway Platform.

Secondary hypothesis: Provider processes and patient depression related outcomes will have greater improvements in patient outcomes after implementation of the App compared to previous practice patterns.

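### Continuous PHQ-9 change and the app-only scales are tested without a comparator, so these tests cannot answer the comparative secondary hypothesis, and PHQ-9 is likely to improve with no Platform effect

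*Combined protocol and SAP*

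**What the plan says.** The secondary hypothesis in 8.1 is comparative: provider processes and depression outcomes "will have greater improvements in patient outcomes after implementation of the App compared to previous practice patterns".

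The analyses of continuous scores are not comparative:

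- For the post-implementation cohort, 8.4 states that "the Pathway Platform will be the data source for paired t-test analysis, assessing change in continuous variables including PHQ-9 scores".
- For PAM-13, CollaboRATE and WSAS, listed as secondary, 8.3.2 states: "The difference in scores between baseline, and 6-month follow up will be compared among patients using the Pathway Platform who completed the following measures". The paired t-test is the natural reading for these three, although 8.4 does not name them beside it.
- For exploratory outcomes, 8.4 states that "continuous outcomes will be compared using Student's Paired t test for single group comparison". Section 8.3.3 lists PHQ-9, WHO-5 and PDQ-D5 here and says "This will be restricted to patients who completed these scales at these two-time points", with first versus last score as an addition.
- All tests are two-sided at p<0.05.

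Section 8.4 also names an independent-groups t-test for continuous outcomes, but 8.3.2 lists no continuous PHQ-9 outcome for comparison between cohorts. PHQ-9 is compared between cohorts only as remission and response, and 8.3.2 warns that pre-implementation data on these will be limited.

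On entry, criterion 4 in 4.1 reads: "Patients with inadequate response or tolerability concerns determined based on A PHQ-2 score of 3 or greater", or a lower PHQ-2 with a PHQ-9 of at least 5, recorded in the past 6 weeks or at screening. Criterion 3 requires an antidepressant start, switch or dose change in the past 3 months. On training, 4.4.3 states: "Care team members who manage depression must complete specific training before they are able to enroll patients".

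**The concern.** A paired test in one group asks whether the patients changed. The hypothesis asks whether they improved more than under previous practice. No comparator, benchmark change or adjustment links the two.

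The gap matters most for PHQ-9. Patients enter when symptomatic and soon after a drug change. Response to that change, natural course and regression to the mean would all lower later scores with or without the Platform. WSAS plausibly follows, on the assumption that functioning tracks symptoms. A small p-value would then be easy to read as support for the secondary hypothesis although it says nothing about it.

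PAM-13 and CollaboRATE raise a narrower issue. Their change is also uncontrolled, and the Day 1 rating comes after the care team's required initial training, so any effect of that training already present at Day 1 is not in the change score.

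**Working it through.** **1. The plan's own figure.** The only power basis is the primary outcome (8.2): 75% versus 90%, 80% power, two-sided 0.05.
n = [1.960·√(2·0.825·0.175) + 0.842·√(0.75·0.25 + 0.90·0.10)]² / 0.15² = (1.053 + 0.443)² / 0.0225 ≈ 99.5, so 100 per group, as stated. The increase to 200 per group is for subgroup analyses. No calculation is given for the paired tests.

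**2. Sensitivity of the paired test to drift.** Let d be the mean change not caused by the Platform, divided by the SD of change. The test statistic is noncentral t with noncentrality d·√n.

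- n=200: the critical value is 1.972, so any observed change above 1.972/√200 = 0.14 SD is significant. With d=0.2 the noncentrality is 2.83 and the rejection probability 0.80; with d=0.1 it is 0.29; with d=0 it is 0.05.
- n=100 completers: the threshold is 0.20 SD, and d=0.2 gives 0.51.
- In points, assuming an SD of PHQ-9 change of 5 to 7 (not in the documents): a 1-point fall unrelated to the Platform is significant with probability 0.52–0.80 at n=200 and 0.29–0.51 at n=100. A 2-point fall gives 0.98–1.00 and 0.81–0.98.

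**3. The same drift with a comparator.** In 20,000 simulated trials of two cohorts of 200 with equal drift of 0.2 or 0.5 SD, an independent-groups t-test rejected 4.7% and 5.2% of the time. The one-group test rejected 81% and 100%.

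**4. Regression to the mean alone.** Assumptions: PHQ-9 approximately normal in the source population, mean 8–10, SD 6, entry at 5 or more (4.5 on the continuous scale), no true change. Entry through PHQ-2 is not modelled. Put c = (4.5 − mean)/6 and λ = φ(c)/[1 − Φ(c)]. This gives λ = 0.3365/0.7202 = 0.467 for mean 8, and 0.2621/0.8203 = 0.320 for mean 10.

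*(a) Qualifying score used as baseline.* With correlation ρ between baseline and follow-up, fall = 6(1−ρ)λ and SD of change = 6√[(1−ρ)²v + 1 − ρ²], where v = 1 + cλ − λ² (0.509 for mean 8, 0.605 for mean 10). The range for ρ is 0.5 to 0.84. The upper value is the app-versus-paper correlation quoted in 2.1; a six-month correlation is likely lower.

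| Mean | ρ | Fall (points) | SD of change | P(significant improvement), n=100 | n=200 |
|---|---|---|---|---|---|
| 8 | 0.5 | 1.40 | 5.62 | 0.70 | 0.94 |
| 8 | 0.84 | 0.45 | 3.33 | 0.27 | 0.48 |
| 10 | 0.5 | 0.96 | 5.70 | 0.39 | 0.66 |
| 10 | 0.84 | 0.31 | 3.34 | 0.15 | 0.25 |

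*(b) Separate app baseline.* Fall = 6(r₁ − r₂)λ, where r₁ and r₂ are the correlations of the qualifying score with the app baseline and with follow-up.

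- If r₁ = r₂ (for example 0.7), the fall is 0 and the probability is the nominal 0.025. All the regression happens before baseline.
- If r₁ = 0.8 and r₂ = 0.45, with 0.5 between baseline and follow-up, the fall is 6·0.35·0.467 = 0.98 points for mean 8 (probability 0.66 at n=200) and 0.67 points for mean 10 (0.36). Other correlations move this upper end.

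**5. PAM-13 and CollaboRATE.** Entry does not select on activation or shared decision making, and the documents give no expected drift. At zero drift the test rejects 5% of the time.

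**The case against.** The strongest reply is that the plan already sends hypothesis testing to the right place. Section 8.4 opens by assigning primary and secondary hypotheses to the cohort comparison and introduces the user-only scales as additional; 1.2 says outcomes among users will be explored; continuous PHQ-9 change is exploratory in 8.3.3; and remission and response are compared between cohorts. No sentence says that a significant within-user change will be credited to the Platform. This stands, and it limits the point to a missing comparison and a missing statement of interpretation. It does not remove the point: three of the scales are classed as secondary, p<0.05 is attached to every test, and nothing tells the reader what these tests cannot show.

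A reader might infer several stronger things that the documents do not support:

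- *That clinician training makes a significant change expected with an inert Platform.* Section 4.4 makes education one of the Platform's three components, although the synopsis names only the app and the care team interface. An effect already present at baseline also does not create later change.
- *That change from baseline cannot capture education at all.* Audit and feedback sessions, the online resource center and in-app education can continue after Day 1. Only the initial training must come first.
- *That significance is expected for PAM-13 and CollaboRATE.* Nothing in the entry criteria or the documents' figures shows this.
- *That regression to the mean must inflate the PHQ-9 test.* The qualifying score may be up to 6 weeks old and the app baseline is a separate measurement, so the inflation can be nil. The PHQ-9 argument then rests on the recent drug change and natural course, for which the documents give no size.

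It is also fair to say that a 95% CI excluding zero carries the same information as p<0.05. The gain comes from the added comparator and the stated limit on interpretation, not from removing the p-value.

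**Conclusion.** The point holds in a limited form. Continuous PHQ-9 change and the app-only scales have no comparator, so their tests do not address 8.1. For PHQ-9, and plausibly WSAS, improvement without any Platform effect is likely. The test is sensitive enough to declare a small drift significant: 0.2 SD of change about 80% of the time at n=200.

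Regression to the mean contributes 0 to 1.4 points and moves the probability of significant improvement at n=200 from 0.025 to as much as 0.94. The upper end requires the qualifying score to serve as baseline. The SD, source mean, correlations and number of completers are all assumptions. For PAM-13 and CollaboRATE the conclusion is only that change is uncontrolled and starts after initial training. The primary outcome and the planned response and remission comparisons are untouched.

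**What to change.** In 8.4:

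1. Add a pre-versus-post cohort comparison of continuous PHQ-9: last score regressed on cohort and first score, using the first and last scores that 8.3.2 already takes for response, drawn from the EMR in both cohorts. Rest inference about PHQ-9 improvement on this and on response and remission.
2. Report within-user changes in PHQ-9, WSAS, PAM-13, CollaboRATE, WHO-5 and PDQ-D5 as mean change with 95% CI. State that they are uncontrolled, do not test the secondary hypothesis and, for PAM-13 and CollaboRATE, start after initial care-team training.

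The cost is SAP wording and one model, with no new data. No p-value is claimed for the app-only scales.

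The added comparison has a real limit. It uses only patients with two scores, which is the primary outcome itself, so they will be fewer and possibly selected in the pre cohort. On the plan's own rates this is 0.75·200 = 150 against 0.90·200 = 180. With SD 6 and ρ from 0.5 to 0.84, the residual SD is 6√(1−ρ²) = 5.20 to 3.26, and the 95% half-width is 1.96·SD·√(1/150 + 1/180), or about 1.1 to 0.7 points. State the limit and report the number contributing in each cohort. App scores also flow into the EMR (4.4.2), and 2.1 cites app scores running higher than paper, so report the source of each score.

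Do not restrict CollaboRATE change to patients with a visit between ratings: that conditions on a post-baseline event which the Platform may influence.
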